#### 2.4.4.3 Fatigue Impact Scale

The FIS is composed of 40 items that assess the individual's attribution of functional limitations to their subjective experience of fatigue in 3 dimensions.

- 0 - "No problem"
- 1 - "Small problem"
- 2 - "Moderate problem"
- 3 - "Big problem"
- 4 - "Extreme problem"

(Lower score = Less fatigue impact)

Cognitive Dimension Score = sum of items 1; 5; 6; 11; 18; 21; 26; 30; 34; 35

Physical Dimension Score = sum of items 10; 13; 14; 17; 23; 24; 31; 32; 37; 38

Social Dimension Score = sum of items 2; 3; 4; 7; 8; 9; 12; 15; 16; 19; 20; 22; 25; 27; 28; 29; 33; 36; 39; 40

Total Score = sum of all items (1-40)

If up to four items are missing within one questionnaire, these items will be imputed with the median of the available observations of the same questionnaire for the Total Score derivation. If more than four items are missing, the Total Score will be regarded as missing. The dimension scores will only be calculated if all included items are available.

Change in FIS will be tested using linear Mixed Models including all scheduled assessment time points with baseline as a covariate along with the other covariates as used in the primary analysis

#### 2.4.4.4 MSQOL-54

The available software will be used to summarize the questionnaire data. In a first step, SDTM datasets containing response items will be transformed into a file format appropriate to input to the scoring software. The output data of the scoring software will be transformed into ADaM format for statistical analysis.

Change in MSQoL-54 will be tested using linear Mixed Models including all scheduled assessment time points with baseline as a covariate along with the other covariates as used in the primary analysis

#### 2.4.4.5 Time out of work

Diaries will be summarized for periods of approximately 48 weeks and the overall treatment period, calculating, per period:

- Sum of hours worked (not tabulated)

- Sum of hours missed
- Total work hours (worked+missed) (not tabulated)
- Percentage of hours missed (missed / worked+missed).

The percentages of missed work hours will be compared between arms using Wilcoxon rank sum tests.

#### 2.4.4.6 Steroid use

- Number of IRAP confirmed relapses treated with steroid
- Percentage of IRAP confirmed relapses treated with steroid

The number of IRAP confirmed relapses treated with steroid will be analyzed the same way as the primary endpoint.

#### 2.4.4.7 Hospitalization due to (suspected) MS relapse

- Days in hospital due to suspected MS relapse
- Percentage of days in hospital due to suspected MS relapse (with all days in hospital as the denominator)
- Percentage of subjects hospitalized due to suspected MS relapse

#### 2.4.4.9 Immunogenicity

Blood samples will be collected per study protocol for determination of ADA.

f

#### 2.4.4.10 Analysis of other variables

The proportion of subjects hospitalized due to suspected MS relapse and the proportion of subjects receiving steroid as treatment for IRAP confirmed relapse will be analyzed the same way as NEDA.

For analysis of lesion volume related variables (Total volume of Gd enhancing T1 lesions per MRI scan over the treatment period, Volume of T2 lesions, Volume of hypointense T1 lesion component

(black holes)) Mixed Model Repeated Measures (MMRM) analyses will be implemented via [REDACTED]

For every valid MRI, cubic root transformed volumes will be used for analysis. For each time point, the sum of these values for all scheduled post-baseline MRIs, divided by the number of MRIs contributing to this sum will be used as the analysis value. Change from baseline in these cubic root transformed, cumulative values will be analyzed. The descriptive analysis will use the untransformed data.

The models will include factors (fixed effects) for treatment, region, baseline EDSS strata, visit, treatment-by-visit interaction, and baseline value (cubic root transformed). The factor, visit, with nominal visits to avoid undue reliance on a linear in time effect will have 3/4 levels (Week 12 – where applicable - , Week 24, Week 48, and Week 96). An unstructured correlation matrix will be used to model the within-patient errors. Parameters will be estimated using restricted maximum likelihood method with the Newton-Raphson algorithm. Denominator degrees of freedom will be estimated using Satterthwaite's approximation.

Time to first confirmed relapse is defined as (date of relapse onset – date of randomization + 1) and will be regarded as censored at the end of treatment. The analysis will be similar to the one of time to confirmed disability progression. The Nelson–Aalen estimator is a non-parametric estimator of the cumulative hazard rate function in case of censored data or incomplete data and will be provided for descriptive purposes.

The proportions of subjects with a relapse and subjects free of disability progression at different time points will be estimated using the Kaplan-Meier method.

#### 2.4.5 Analyses of Safety Data

Safety results will be summarized and presented by treatment group.

##### **Observation period**

The observation period is defined as the time from first dose of study medication up to 20 weeks after the last dose of study medication or until the final subject completes the Week 96 assessment.

##### **General common rules**

All safety analyses will be performed on the Safety Population as defined in Section 2.2.1, unless otherwise specified, using the following common rules:

1. For quantitative safety parameters based on central laboratory/ reading measurements, visit and treatment group will use descriptive statistics to summarize results and change from baseline values. Summaries will include the value and/or the worst value of the observation period.
2. All of the values including unscheduled measurements will be assigned to the appropriate safety analysis visit window. The safety analysis visit window is defined in Section 2.5.2. In the presence of multiple measurements of the same test in the same window, the one closest to the targeted visit date will be used for the by-visit summaries.

3. The analysis of the safety variables will in general be descriptive and no systematic statistical testing is planned.

#### 2.4.5.1 Analysis of Adverse Events

##### **Adverse event classification:**

1. Pre-existing AEs are defined as adverse events that started prior to treatment start and are ongoing at the time of treatment start. After treatment start, if these adverse events worsened during the treatment period these will be considered as treatment-emergent adverse events (TEAEs).
2. TEAEs are defined as AEs with an onset on, or after the first dose of study medication and through 30 days after the last dose of study medication or with an onset prior to the first dose of study medication that increases in severity on, or after the first dose of study medication and through 30 days after the last dose of study medication.
3. Post-treatment AEs are defined as AEs that developed or worsened during the post treatment period after stopping study medication. As an example, AEs occurring during the 20-week follow-up involving rapid teriflunomide/oral placebo elimination would be considered a post-treatment AE.

Data will be analyzed as available in the database as not all subjects are expected to be followed up for the full period e.g. due to switch to the open-label extension.

Adverse event incidence tables will be presented by treatment group, the number (n) and percentage (%) of subjects experiencing an AE. The incidence of events will be presented: A subject will only be counted once in the tables within a treatment phase. In a subset of tables, also all occurrences will be counted providing a severity of occurrence of the AE. The denominator for computation of percentages is the Safety Population within each treatment group.

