Study Rationale	
Over the past decade, the understanding of the role of B and/or T cells in autoimmune diseases has been of great priority in both pre-clinical and clinical research in autoimmune diseases, especially in multiple sclerosis. In multiple sclerosis, B cells can form autoantibodies, which can result in pathological immune complex depositions that can activate the complement system as well as initiate acute inflammatory cascade by producing pro-inflammatory cytokines and chemokines. Further, B cells have been shown to regulate the formation and function of T cells, which can aid in the demyelinating events seen with multiple sclerosis.
 
Ublituximab (also known as TG-1101) is a monoclonal antibody that specifically binds to the trans-membrane antigen CD20 found on B-lymphocytes. The binding of ublituximab induces an immune response that causes lysis of B cells. Ublituximab has a unique protein sequence, and targets epitopes on CD20 not targeted by rituximab, ofatumumab, or ocrelizumab; anti-CD20 antibodies approved or in development for oncologic diseases and autoimmune disorders. The CD20 molecule is expressed on pre-B cells and throughout the lifecycle of both naïve and memory B cells. It is not expressed on stem cells or pro-B cells at the earliest stages of B cell differentiation. Further, it is not expressed on plasmablasts or terminally differentiated plasma cells. [8] Thus, CD20 is an ideal target for B cell targeted immunotherapy.
 
Rituximab was the first anti-CD20 monoclonal antibody (mAb) tested in relapsing forms of Multiple Sclerosis (RMS) subjects. More recently, ocrelizumab, a humanized anti-CD20 monoclonal antibody has shown promising results in its two Phase III trials (OPERA I and OPERA II) [20]. In OPERA I and II, subjects treated with ocrelizumab had significantly lower Annualized Relapse Rates (0.156 and 0.155, respectively) compared to subjects treated with IFNβ-1a 44μg (0.292 and 0.29, respectively). Further, in OPERA I and II, subjects treated with ocrelizumab had approximately 46% reduction in ARR as compared to those treated with IFNβ-1a 44μg; TG Therapeutics is powering this study for a 40% reduction in ARR.
 
TG Therapeutics has performed a Phase 2a clinical trial using ublituximab as a single agent to examine the level of B cell depletion by ublituximab as well as determine the optimal dose and infusion time for ublituximab in subjects with RMS. Based on the results of the Phase 2a study with a dosing of 150 mg (infused for 4 hours) on Week 1 Day 1 and a dosing of 450 mg (infused for 1 hour) on Week 3 Day 15, a median of >99% B cell depletion was achieved on Week 4 and sustained until Week 24. The dosing regimen was well tolerated by the subjects with Infusion Related Reactions (grade 1 and 2) being the commonly reported adverse event.
 
TG Therapeutics also performed a Phase 1 clinical study using ublituximab as a single agent to examine the safety and tolerability of a single dose ublituximab at 450 mg in subjects diagnosed with acute Neuromyelitis Optica (NMO) relapse. Although the single dose of 450 mg ublituximab infused for 4 hours was safe and well tolerated, the

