In case of an IRAP-confirmed MS relapse (as defined in the protocol, Appendix C) or Treating Neurologist medically confirmed relapse during the study, the following actions will be taken:

- The subject will be reminded of the current approved MS medications/treatments and the opportunity to terminate the study and be treated with an approved MS medication.
- The subject will be requested to re-sign an informed consent form within 6 weeks after first reporting of the suspected relapse if he/she chooses to continue to participate in the study, in the same treatment assignment.

[figure not shown]
Disability Progression

The method of disability progression calculation will be different than that of the relapse confirmation. The EDSS score will be used to assess disability progression. EDSS assessment will be performed by the Examining Neurologist. The Examining Neurologist must not share the EDSS score with the Treating Neurologist. The EDSS assessment for disability progression will be performed at screening and on Week 1 Day 1 (prior to randomization) and Weeks 12, 24, 36, 48, 60, 72, 84 and 96. To clarify, disability progression is not calculated by the Examining Neurologist (disability progression is a post hoc analysis based on the EDSS scores).

Disability progression is defined as an increase of ≥ 1.0 point from the baseline EDSS score that is not attributable to another etiology (e.g., fever, concurrent illness, or concomitant medication) when the baseline score is 5.5 or less, and ≥ 0.5 when the baseline score is above 5.5. Disability progression is considered confirmed when the increase in the EDSS is confirmed at regularly scheduled visits at least 12 or 24 weeks after the initial documentation of neurological worsening.

Treatment Study Visits

Ublituximab/oral placebo vs Teriflunomide/IV placebo Regimen (please see dosing regimen below)

- Ublituximab or IV placebo: Infusions on Week 1 Day 1 and Week 3 Day 15 and Weeks 24, 48, and 72
- Teriflunomide or oral placebo: Daily starting at Week 1 Day 1 until the last day of Week 95

Abbreviated Blood Sample Assessment Schedule (for further details see Section 6):

- For all subjects treated:
 - Blood collection for CBC and serum chemistry at screening, and Week 1 Day 1 (pre-dose), Week 1 Day 2, Week 2 Day 8, Week 3 Day 15 (pre-dose), and Weeks 4, 8, 12, 16, 20, 24 (pre-dose), 36, 48 (pre-dose), 60, 72 (pre-dose), 84 and 96

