9.5 TREATMENT EMERGENT ADVERSE EVENTS (TEAE'S)

The frequency and percentages of subjects with treatment-emergent adverse events (TEAEs) will be tabulated by system organ class (SOC) and preferred term (PT), where treatment-emergent is defined as any AE with an onset on or after the first dose of study medication and through 30 days after the last dose of study medication or with an onset prior to the first dose of study medication that increases in severity on, or after the first dose of study medication and through 30 days after the last dose of study medication.

In addition, TEAEs that are considered at least possibly related to study treatment will be tabulated as well as deaths, SAEs, and events resulting in treatment discontinuation or termination. Additionally, the subset of events which occurred after the last study drug administration will be summarized.

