#### 2.1.3.1 Primary Efficacy Variable

The primary efficacy variable (per patient) is the number of IRAP-confirmed relapses (recorded in the eCRF as “Was the relapse adjudicated as protocol defined relapse by IRAP?”=Yes) which started (Start Date of Suspected Relapse Symptoms) on or after the day of randomization and up to the day of last study treatment. If the exact start date of relapse symptoms is unknown, the relapse will be assumed to have started during this period unless sufficient information is available to conclude that the symptoms started before or after (e.g. in case of missing start day, the symptoms start month is after the month of treatment end).

Annualized Relapse Rate will be summarized within treatment group as the ratio of the sum of all patients’ relapse counts divided by the sum of all patients’ treatment duration (in years). Years under treatment will be derived as:

Treatment years =  $(\text{date of last treatment intake (oral or IV)} - \text{date of randomization} + 1) / 365.25$ .

The statistical testing approach is described in section 2.4.3.1.

Please see below for the assessment process of suspected relapses.

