##### **Not treatment emergent AE(s) summary:**

- Listing of (not treatment emergent) AEs showing treatment group, subject identifier, SOC, PT, verbatim term, date and day of onset, end date/time, duration, outcome, severity, date of death (if relevant), relationship to study treatment, action taken, AE seriousness and criteria.

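### The SAP puts adverse events starting more than 30 days after the last dose only in a listing, although they are collected for 20 weeks and Protocol 9.5 promises a summary of post-treatment events

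*SAP*

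**What the plan says.** Both documents use the same window. SAP 2.4.5.1 (Adverse event classification) reads "TEAEs are defined as AEs with an onset on, or after the first dose of study medication and through 30 days after the last dose", and Protocol 9.5 has the same rule. Collection runs longer: Protocol 9.6.1 and 9.6.3 require adverse events to be recorded for 20 weeks after treatment ends, and SAP 2.4.5 sets a matching span: "The observation period is defined as the time from first dose of study medication up to 20 weeks after the last dose".

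The outputs differ. Protocol 9.5 adds that "the subset of events which occurred after the last study drug administration will be summarized". SAP 2.4.5.1 names a class of post-treatment adverse events, but the only output it specifies outside the treatment-emergent class is a "Listing of (not treatment emergent) AEs showing treatment group, subject identifier" and further descriptors. The overview, SOC/PT, related, AESI, suicidality, serious and discontinuation tables are all restricted to treatment-emergent events. Deaths are the exception, being counted by treatment group over the study period.

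On timing, the Protocol Synopsis (Treatment Study Visits) gives the IV schedule as "Infusions on Week 1 Day 1 and Week 3 Day 15 and Weeks 24, 48, and 72" and the oral schedule as "Daily starting at Week 1 Day 1 until the last day of Week 95". The Study Rationale reports that in Phase 2a "a median of >99% B cell depletion was achieved on Week 4 and sustained until Week 24". Under Protocol 6.10, the 11-day teriflunomide elimination starts the day after the withdrawal visit for early discontinuers and at Week 100 for completers.

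**The concern.** A window for treatment-emergent events should roughly cover the time a drug is still acting. Thirty days is short for an antibody infused every 24 weeks. A subject who stops both drugs soon after an infusion may be B cell depleted for months. An infection or serious event in that time would be collected but would enter no by-arm adverse event table.

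Comparative safety by adverse events and serious adverse events is a stated secondary objective, and Protocol 6.10 gives safety monitoring as a purpose of the follow-up. For rare serious events and infections a handful of cases can change the picture, and a listing gives the reader neither a denominator nor a rate.

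**Working it through.** The plan states no figure to reproduce, so the check is arithmetic on the timeline.

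**Inputs from the documents**
- Infusions on Days 1, 15, 168, 336 and 504. From Week 24 the interval is 504 − 336 = 168 days (24 weeks).
- Last oral dose at the end of Week 95: 95 × 7 = Day 665.
- Follow-up from Day 672 to Day 812 = 140 days (20 weeks).
- Window after last dose: W = 30 days = 4.29 weeks.
- 220 subjects per arm (Protocol 8.1, SAP 1.3). A 10% dropout allowance and 1.75 years' average observation (Protocol 8.8, SAP 1.3.1).

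**Assumptions**
- Early discontinuers stop both drugs on one day, u weeks after the last infusion, with u uniform on 0–24.
- Drug effect lasts L weeks. The base case is L = 24, from Phase 2a. A single-dose neuromyelitis optica study saw repletion begin after 3 months, so L = 13 is the low case and L = 36 the high case.

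**Step 1: length of the window.** 30/168 = 18% of the dosing interval and 30/140 = 21% of the follow-up.

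**Step 2: completers on ublituximab.** The window ends at Day 665 + 30 = 695, which is 695 − 504 = 191 days (27.3 weeks) after the Week 72 infusion. The whole 24-week interval is covered.

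**Step 3: early discontinuers on ublituximab.** Time under effect but outside the window is max(0, L − u − W). Its mean over u is (L − W)²/48 for L up to 24, and L − 12 − W for L = 36. Mean time under effect after stopping is L²/48 for L up to 24, and L − 12 for L = 36.

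| L (weeks) | Mean weeks outside window | Mean post-stop weeks under effect | Share of post-stop time | Share of whole effect period (outside/L) |
|---|---|---|---|---|
| 13 | 1.58 | 3.52 | 45% | 12% |
| 20 | 5.14 | 8.33 | 62% | 26% |
| 24 | 8.10 | 12.00 | 67% | 34% |
| 36 | 19.71 | 24.00 | 82% | 55% |

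At L = 24, stopping on an infusion day is the worst case: (24 − 4.29)/24 = 82% of the effect period is outside. Nothing is lost when u is at least 24 − 4.29 = 19.7 weeks. More than half of the post-stop time is lost only when u is below 24 − 2 × 4.29 = 15.4 weeks.

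**Step 4: size within an arm.** If 10% of 220 = 22 subjects stopped early and were followed, 22 × 8.10 = 178 person-weeks fall outside (worst case 22 × 19.71 = 434). Arm person-time is 220 × 1.75 × 365.25/7 = 20,089 person-weeks. The shares are 0.9% and 2.2%.

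**Step 5: the other arm.** For teriflunomide completers the window ends about Day 695, but elimination runs from Day 700 to Day 710. With 220 − 22 = 198 completers, 198 × (710 − 695)/7 = 424 person-weeks with drug not yet eliminated also lie outside, fewer if subjects move to the extension.

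**The case against.** The strongest reply is that the window is prespecified, identical in both arms and consistent across the documents, for safety analyses that SAP 2.4.5 calls descriptive. That is fair: 30 days can stand as the definition of treatment-emergent. It does not explain why the SAP drops a summary the protocol announces. One could read the Protocol 9.5 sentence narrowly, as covering only treatment-emergent events after the last dose, but the SAP has no such table either. Its remark about counting subjects once within a treatment phase does not create one.

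Several stronger readings are tempting, and the documents do not support them.
- *The comparison favours ublituximab.* The direction is plausible among early discontinuers, because only teriflunomide is actively removed. Step 5 shows loss in the other arm too, and Protocol 6.10 lets subjects who withdraw consent decline elimination. No discontinuation or late event rates by arm are given.
- *Most events under drug effect are lost.* No event rates are given. In time, the base-case loss is a third of the effect period. The clock runs from the last study medication, which includes the daily tablet in both arms, and the 18% figure applies only if both drugs stop on an infusion day.
- *About 22 subjects per arm are affected.* The 10% is a sample-size allowance for dropout. Under Protocol 3.3, data collection stops at withdrawal of consent unless the subject signs the early termination consent, so some dropouts have no later events to tabulate.
- *Late safety data reach no by-arm table at all.* Deaths do, abnormal vital signs are summarized over the observation period (SAP 2.4.5.3), and laboratory toxicity over any post-baseline assessment (SAP 2.4.5.2). The gap concerns tables of non-fatal adverse events.

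**Conclusion.** The concern stands in limited form. The SAP does not carry out the post-treatment summary in Protocol 9.5, so non-fatal adverse events and serious adverse events starting between Day 31 and Week 20 after the last dose appear in no by-arm adverse event table. This omission needs no pharmacological assumption.

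What it costs does rest on assumptions. With a 24-week effect and uniform stopping, about 8 weeks per followed early discontinuer on ublituximab fall outside the window. The 1–2% share of arm person-time further treats the 10% dropout allowance as followed discontinuers. Ublituximab completers are covered. The net direction between arms is undetermined.

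The amount is small, but the change should be made: the data exist, and late serious events and infections are where a few cases matter.

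**What to change.** In SAP 2.4.5.1, keep the 30-day treatment-emergent tables and add by-arm incidence tables of all adverse events, serious adverse events and AESIs (including infections). These should run from first dose to 20 weeks after last dose and stop at the first open-label extension dose. Give rates per person-year as well, since the SAP notes that extension entrants have shorter follow-up.

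Three clarifications are needed:
- Define last dose for safety as the later of oral or IV. SAP 2.1.3.1 says so only for the primary endpoint.
- Resolve the observation period in SAP 2.4.5, which also offers an alternative end when the final subject has the Week 96 assessment, without saying which applies.
- Flag events that start during the elimination procedure.

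The cost is a few extra tables from data already collected, with no change to trial conduct. The small downside is that some events caused by the elimination procedure will be included; the flag lets a reader set them aside.
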